4.11.4 Vital Signs

Vital signs data (systolic and diastolic blood pressure, heart rate, temperature, respiration rate, and if available orthostatic drop calculated as standing minus supine value) will be listed for individual subjects.

Summary statistics of absolute (observed) values and changes from baseline will be calculated for each parameter and scheduled time point by treatment.

As per the study protocol, out of range blood pressure or heart rate measurements are to be repeated by the Investigator's discretion, and for summary statistics any such repeated measurement is to be used instead of the initial out of range measurement.

4.11.5 Physical Examination

Physical examination data will be listed individually and abnormal findings will be summarized by period and treatment.

4.12 Pharmacokinetic Analyses

All plasma concentration data will be listed for each individual subject and summarized at each time point by treatment. Individual and mean concentrations versus nominal time on linear and semi-log scales will be presented graphically by treatment

The PK population will be used to present the summary of PK parameters.

4.12.1 Values Below the Limit of Quantification and Missing Values

If a Below the Limit of Quantification (BLQ) value occurs in a profile before the first measurable concentration within period, it will be assigned a value of zero concentration. If a BLQ value occurs after a measurable concentration in a profile and is followed by a value above the lower limit of quantification, then the BLQ value will be omitted following visual inspection of the plasma concentration versus time profile to assess the appropriateness of this assignment. If a BLQ

value occurs at the end of a collection profile (after the last quantifiable concentration), the value will be treated as missing data. If 2 BLQ values occur in succession, the profile will be deemed to have terminated at the first BLQ value and any subsequent concentrations will be omitted from PK calculations following visual inspection of the plasma concentration versus time profile to assess the appropriateness of this assignment.

Samples with no reportable value due to a bioanalytical issue or missing samples will be set to missing, and will not be included in the PK calculations. If a subject vomited following dose administration, then their profile will be examined to determine the impact of this on PK parameter estimation.

When calculating the mean or median value for a concentration at a given time point, all BLQ values will be set to zero except when an individual BLQ falls between 2 quantifiable values, in which case it will be omitted.

For tabulation, graphical representation, and calculation purposes, all samples with no reportable value (or missing samples) observed after dosing will be set to missing.

4.12.2 Pharmacokinetic Parameters

The plasma total Mo PK parameters will be summarized with descriptive statistics.

Analyses of other PK data including, but not limited to those, of PUF Mo may be conducted. PK parameters will be calculated using Phoenix® WinNonlin®.

The following PK parameters will be derived for each subject:

- C_{max} [ng/mL]: Maximum observed plasma concentration
 - \circ for multiple peaks, the highest post-dose concentration will be reported as C_{max}
- **T**_{max} **[h]:** Time to maximum observed plasma concentration
 - \circ in case that multiple peaks are of equal magnitude, the earliest T_{max} will be reported
- **AUC**_t [h*ng/mL]: Area under the plasma concentration versus time curve from time zero (dosing) to the last quantifiable concentration
- AUC_{∞} [h*ng/mL]: Area under the plasma concentration versus time curve from time zero (dosing) extrapolated to infinity
- AUC_{extr} (%): The percentage of AUC_∞ extrapolated
 - \circ Subjects with an AUC_{ext} > 20% will be flagged, and parameters that are dependent on AUC ∞ will also be flagged (AUC ∞ , AUC ∞ _n, CL/F, Vd/F and F_{rel})
- λ_z [1/h]: Apparent terminal-phase elimination rate constant

- only those data points that are judged to describe the terminal loglinear decline will be used in the regression.
- \circ A minimum number of 3 data points in the terminal phase will be used in calculating λ_z , with the line of regression starting at any post- C_{max} data point (C_{max} should not be part of the regression slope).
- t_{1/2} [h]: Terminal elimination half-life
 - \circ Calculated as In(2) / λ_z
- CL/F [L/h]: Apparent total clearance
 - Calculated as dose / AUC_∞.
- Vd/F [L]: Apparent volume of distribution during terminal phase
 - Calculated as dose / $(\lambda_z * AUC_{\infty})$
- Relative Bioavailability (F_{rel}): defined as the ratio of the geometric means of PK parameter (C_{max}, AUC_t and AUC_∞) for the test (= treatment B = 3 x 5 mg ALXN1840 EC tablets) over the reference (= treatment A = 1 x 15 mg ALXN1840 EC tablet) treatment, for details see section 4.12.3

PK parameters will be listed for each individual subject and summarized by period and treatment. Descriptive statistics for PK parameters will include number of observations (n), arithmetic mean (Mean), SD, arithmetic coefficient CV, geometric mean, geometric CV, median, minimum and maximum.

Some PK parameters may not be calculated for all or some subjects if the concentration data are not deemed to be amenable to evaluation. Explanations for PK parameters that could not be estimated will be provided in the CSR. Additional PK parameters may be calculated, as appropriate.

4.12.3 Bioavailability Analysis

The PK parameters for total Plasma and Plasma Ultrafiltrate Mo (C_{max} , AUC_t, and AUC_{∞}) will be evaluated using an Analysis of Variance (ANOVA) statistical model with dosing period, treatment, and sequence as the fixed effects, and subject as a random effect, using the natural logarithms of the data. Confidence intervals (90%) will be constructed for the least squares geometric mean ratios (GMR) for the 3 × 5 mg ALXN1840 (test) versus 1 × 15 mg ALXN1840 (reference) dose for all 3 parameters using the natural log-transformed data. The GMRs and associated 90% confidence limits will be exponentiated back to the original scale. The within-subject coefficient of variation for the C_{max} , AUC_t, and AUC_{∞} will be estimated using the mean squared error from the ANOVA. In addition, the geometric means and the associated 95% confidence intervals of C_{max} , AUC_t, and AUC_{∞} will be reported for each treatment.

4.12.4 CL/F and Body Size

Relationships between CL/F and body size (body weight [kg] and BMI [kg/m²]) will be evaluated graphically for the two treatment sequences and with combined data. If suggested by the graphs, regression models may be fit to the data.

4.13 Pharmacodynamic and Biomarker Analyses

Individual ALXN1840 PD and biomarkers, assessed as plasma total Cu (PD), NCC (PD), NCC $_{\rm corrected}$ (PD), Cp (biomarker), and CpC (biomarker) concentration-time data (including measured, absolute and percent changes from baseline) will be listed and summarized at each time point by treatment with descriptive statistics.

NCC is calculated by subtracting the amount of Cu bound to ceruloplasmin from the total plasma Cu level:

$$NCC[\mu mol/L] = \frac{Total\ plasma\ Cu\ [\mu g/L] - (3.15*ceruloplasmin\ [mg/L])}{63.5\ [\mu g/\mu mol]}$$

For subjects dosed with ALXN1840, there is also Cu bound in the tetrathiomolybdate-Cu-albumin tripartite complex which is addressed by the NCC correction method:

$$NCC_{corrected} = (\sqrt{NCC} - 0.993\sqrt{Mo})^2$$

In the calculation of NCC and NCCcorrected, the following adjustments will be made:

- Copper values < lower limit of quantification (LLOQ) are set to missing and NCC will not be derived;
- Ceruloplasmin <LLOQ are set to 0;
- Molybdenum <LLOQ are set to 0;
- Negative NCC values are not utilized and NCCcorrected will not be derived;
- NCCcorrected will be set to 0 when $0.993\sqrt{Mo} > \sqrt{NCC}$.

Individual subject data (and change from baseline) of plasma Cp and copper levels (total Cu, Cp, CpC and NCCcorrected) will be presented graphically for each period and treatment. Mean plots (for measured and change from baseline value) by period and treatment will be presented (separately for PD and biomarker parameters) and over time by period.

Analyses of other biomarker data including, but not limited to, those of PUF Cu may be conducted.

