2.2 Endpoints

Primary

• PK parameters for plasma total molybdenum (Mo) including the maximum observed plasma concentration (C_{max}), the area under the plasma concentration versus time curve from zero to the last quantifiable concentration (AUC_t), and extrapolated to infinity (AUC_{∞}).

Secondary

 Safety assessed by incidence of treatment emergent adverse events (TEAEs) and serious TEAEs (TESAEs), physical examination, vital signs measurements, clinical laboratory, and 12-lead electrocardiogram (ECG) results.

Exploratory

- CL/F, body weight, and body mass index.
- Absolute and percent changes of plasma copper (Cu) levels including total Cu, ceruloplasmin (Cp), ceruloplasmin-bound copper (CpC) and nonceruloplasmin-bound copper (NCC).
- The NCC level will be corrected for the amount of Cu bound to the TPC resulting in corrected NCC (NCC_{corrected}).

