Baseline will be defined as the last non-missing value among assessments recorded prior to first administration of study drug per period, where unscheduled assessment at the respective scheduled study are also taken into account. Changes from baseline values will be calculated as the post-baseline assessment value minus the baseline value per period. In general, only observed values from scheduled time points will be used to create summary tables, with the exception of unscheduled assessments on the respective study day. It is assumed that unscheduled assessments on scheduled study days are repetitions of potentially invalid scheduled assessments, and thus those unscheduled assessments will replace the respective scheduled assessments for summary tables and further statistical analyses.

Early Termination (ET) visits will be recoded to ET visits where necessary and reported as ET.

Deviations from the planned analyses will be described in the final clinical study report (CSR).

Page layout of the TFLs will be in landscape mode and will be provided as RTF files in Microsoft Word. Final TFLs will additionally be created in bookmarked portable document format (PDF). Further details of page layout will be provided in the TFL shell document.

All statistical analyses will be conducted using SAS® for Windows® Version 9.3 or higher.

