4.14 Methods for Withdrawals, Missing Data and Outliers

The individual plasma concentration data and the actual timing of study drug administration and blood sampling will be used throughout the analyses. If there is any doubt about the actual time at which a sample was taken, then the scheduled time will be used. For PK data analysis, please see Section 4.12.1 regarding the handling of missing and below level of quantification (BLQ) values.

For PD data analysis, there will be no imputation for missing values.

If medication dates are incomplete and it is not clear whether the medication was concomitant, it will be assumed to be concomitant.

AEs with unknown start date/time will be assumed to be treatment-emergent unless the end date/time is known to be before the first administration of study drug. Otherwise missing or partial dates will be listed as such.

There will be no further imputation of missing data (i.e., subjects who prematurely discontinue from the study will not be included in summary statistics or analyses beyond the time of discontinuation).

Depending on the extent of missing values, the appropriateness of the methods described for handling missing data may be reassessed prior to database lock (to examine the sensitivity of results to handling of missing data).

Certificate Of Completion

Envelope Id: PPD

Subject: Please DocuSign: C18054 ALXN1840-HV-104 SAP Final 1.0 11Nov2019 signed.pdf

Source Envelope:

Signatures: 2 Document Pages: 20 Certificate Pages: 2 Initials: 0

AutoNav: Enabled

Envelopeld Stamping: Disabled

Time Zone: (UTC-05:00) Eastern Time (US & Canada)

Status: Completed

Envelope Originator:

PPD

[name]

Sent: 19-Nov-2019 | 13:00 Viewed: 19-Nov-2019 | 13:20 Signed: 19-Nov-2019 | 13:21

Sent: 19-Nov-2019 | 13:00

PPD

IP Address: PPD

Record Tracking

Holder: PPD Status: Original Location: DocuSign

19-Nov-2019 | 12:54

Signature Signer Events **Timestamp**

Security Level: Email, Account Authentication

(Required), Digital Certificate

Alexion Pharmaceuticals Inc.

Signature Provider Details: Signature Type: Alexion Pharmaceuticals, Inc.

(Regulated) (Client ID: PPD

PPD

PPD

Signature Issuer: Alexion Pharmaceuticals Issue https://dswebapp.alexion.com/takepen/signenvelope 2 CA

Signature Adoption: Pre-selected Style

Signature ID:

PPD

Using IP Address: PPD

Signature Provider Location:

With Signing Authentication via DocuSign password

With Signing Reasons (on each tab):

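### Discarding negative NCC values biases mean NCC upward whenever they occur and distorts changes from baseline, in an exploratory endpoint

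*SAP*

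**What the plan says.** SAP 4.13 describes the derivation: "NCC is calculated by subtracting the amount of Cu bound to ceruloplasmin from the total plasma Cu level". The formula is (total Cu in µg/L − 3.15 × Cp in mg/L) / 63.5. The corrected version is NCCcorrected = (√NCC − 0.993√Mo)². The adjustments listed with it include:

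- "Molybdenum <LLOQ are set to 0", so NCCcorrected equals NCC when molybdenum is not quantifiable;
- "Negative NCC values are not utilized and NCCcorrected will not be derived";
- "NCCcorrected will be set to 0 when" 0.993√Mo exceeds √NCC.

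SAP 4.14 adds: "For PD data analysis, there will be no imputation for missing values". SAP 4 defines change from baseline within period: "Changes from baseline values will be calculated as the post-baseline assessment value minus the baseline value per period". Protocol Table 2 marks one pre-dose PD sample, at −0.5 h, and 18 post-dose samples per period (8 from 1 to 12 h on Day 1, 10 from 24 to 240 h).

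The endpoint is listed as exploratory in SAP 2.2: "Absolute and percent changes of plasma copper (Cu) levels including total Cu, ceruloplasmin (Cp), ceruloplasmin-bound copper (CpC) and nonceruloplasmin-bound copper (NCC"). SAP 4.13 summarizes it descriptively by time point and treatment.

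**The concern.** NCC is a difference between two measured quantities. When true NCC is small relative to the error of that difference, some calculated values will fall below zero by chance. Deleting those and keeping the matching high values truncates the error distribution on one side. The resulting missingness depends on the value itself.

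Baseline makes this worse. With one scheduled pre-dose sample, a negative pre-dose NCC leaves no baseline unless an unscheduled pre-dose value exists, and up to 18 post-dose changes go with it, for NCC and NCCcorrected alike. Post-dose, a low NCCcorrected may instead be retained as 0. Low values are therefore dropped at one end of the change and kept at the other.

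At stake are the NCC and NCCcorrected means and changes by time point. These will be read as the copper response to 15 mg. Protocol 2.2 cites a 72% reduction in mean serum NCC as evidence of drug effect in patients.

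**Working it through.** **Inputs.** The rules come from SAP 4, 4.13 and 4.14. The documents give no copper or ceruloplasmin level, no assay precision and no expected rate of negative values, so there is no stated NCC figure to reproduce. All levels and error SDs below are assumptions. Errors are taken as normal and, for changes, independent between time points.

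**1. Mean NCC.** For true mean μ and error SD σ, the discarded fraction is Φ(−μ/σ) and the retained mean is μ + σ·φ(μ/σ)/Φ(μ/σ).

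| μ/σ | Discarded | Bias in mean |
|---|---|---|
| 3 | 0.1% | +0.1% |
| 2 | 2.3% | +2.8% |
| 1.5 | 6.7% | +9.3% |
| 1 | 15.9% | +29% |
| 0.5 | 30.9% | +102% |

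At a ratio of 1, for example, 0.2420/0.8413 = 0.288.

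**2. In concentration units.** With the same CV on both assays, σ = CV × √(Cu² + (3.15·Cp)²) / 63.5.

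- Cu 1000 µg/L, Cp 300 mg/L: NCC = (1000 − 945)/63.5 = 0.87 µmol/L. CVs of 3%, 5% and 8% give 9%, 21% and 31% negatives and retained means of 0.98, 1.26 and 1.75.
- Cu 1000 µg/L, Cp 250 mg/L: NCC = (1000 − 787.5)/63.5 = 3.35 µmol/L. Over the same CVs at most 2% are negative and the bias is at most about 0.07.

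A plausible-looking shift in ceruloplasmin therefore moves the problem from substantial to trivial.

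**3. Change in uncorrected NCC.** The retained mean responds to the true mean with slope Var(X | X > 0)/σ², which is 0.63 at μ/σ = 1 and 0.89 at 2. From a baseline mean of 1 with σ = 1 (retained mean 1.288):

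- true +1.0: 2.055 − 1.288 = +0.77;
- true −0.5: 1.009 − 1.288 = −0.28.

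Rises and falls are both attenuated under equal σ. If the post-dose σ is 1.3 times baseline, no true change appears as +0.21 and a true +0.5 as +0.52, so attenuation is not general.

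**4. Change in NCCcorrected.** This was simulated under the SAP rules, with pre-dose molybdenum taken as not quantifiable, post-dose molybdenum of 0.3 or 1.0 in the formula, baseline mean 1 and σ = 1:

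| True change | Under the SAP rules |
|---|---|
| 0 | −0.23 to −0.25 |
| −0.5 | −0.66 to −0.73 |
| −0.8 | −0.88 to −1.00 |

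Falls are exaggerated because low baselines are dropped while low post-dose values stay in. Nearly all of this comes from the baseline deletion: replacing the 0 by the unfloored square changes these results by at most about 0.012. With σ = 0.5 the error is about 0.02 or less, and with baseline mean 2 it is at most about 0.07 in either direction.

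**5. What the 0 rule does.** It does not enter NCC. For NCC 0.25 and Mo 1 the formula gives (0.5 − 0.993)² = +0.243, a positive value produced by squaring an over-correction. The SAP sets it to 0.

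**The case against.** The case for leaving the plan alone has real content.

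- **The two situations differ mathematically.** With negative NCC the square root is undefined. With over-correction the formula is defined but returns a spurious positive value, which the 0 rule prevents. A reader might infer that the two cases are equivalent and that the 0 rule is itself a defect. The formula does not support that. The undefined root does not, however, explain why negative values are also dropped from summaries of NCC, where no root is taken.
- **Nothing shows that negatives will be common.** This stands: the size rests wholly on assumed levels and precision.
- **The consequence is limited.** The endpoint is exploratory, with no test. Both treatments deliver 15 mg to the same subjects under the same rule, so much of the bias should cancel between A and B. Total Cu, Cp and the primary molybdenum analysis are untouched. This stands for the A versus B contrast, but the summaries by time point and treatment are not protected by cancellation.
- **It may be handled elsewhere.** The count of non-missing values is reported (SAP 4), missing-data methods may be reassessed before lock (SAP 4.14), and Protocol 9.4.3.1.2 refers detailed PD analyses to a separate data analysis plan that is not among these documents. The count shows a loss but not its cause, and the reassessment is optional and generic.
- **Keeping negatives has a cost for percent change.** A negative baseline reverses its sign, a near-zero one inflates it, and a zero one makes it undefined. This is correct, and the fix has to deal with it.

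**Conclusion.** The point holds in a limited form. Dropping negative NCC biases mean NCC upward whenever negatives occur, and a negative pre-dose value costs the whole set of changes for that subject and period. Changes from baseline are distorted, in a direction that depends on the error structure and on which version of the marker is read.

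A reader might go further and infer that the rule shrinks changes generally and so understates copper lowering. The documents do not support that. Attenuation follows for uncorrected NCC under equal error SD but can fail if error grows after dosing. For NCCcorrected, the version meant to remove copper held in the tripartite complex, falls tend to be exaggerated when baseline is low relative to error.

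Nor can the effect be called large. Its size depends on the unknown ratio of true mean to error SD: negligible at 3 or more, about +29% in mean NCC at 1. This assumes symmetric, roughly normal error. The impact is confined to an exploratory descriptive endpoint.

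**What to change.** Revise SAP 4.13 as follows.

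- Keep signed NCC as calculated in absolute NCC summaries and absolute changes from baseline. Under symmetric error these are then unbiased.
- Report the number of negative NCC values and of floored NCCcorrected values by time point and treatment.
- Show the current exclusion rule as a sensitivity summary.
- Report percent change only for positive baselines, with the number excluded.
- For NCCcorrected, keep the existing 0 rule and add a sensitivity summary that also sets NCCcorrected to 0 when NCC is negative. State that flooring leaves some upward bias: with mean 1, SD 1 and no quantifiable molybdenum, the floored mean is 1 × 0.841 + 0.242 = 1.083 (+8%, against +29% under deletion). With mean 0.5 and SD 1 it is 0.5 × 0.691 + 0.352 = 0.698 (+40%, against +102%).

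The cost is SAP wording, a few extra summaries, and some physically implausible negative values in the listings. No additional samples or data are needed.

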4.14 Methods for Withdrawals, Missing Data and Outliers

The individual plasma concentration data and the actual timing of study drug administration and blood sampling will be used throughout the analyses. If there is any doubt about the actual time at which a sample was taken, then the scheduled time will be used. For PK data analysis, please see Section 4.12.1 regarding the handling of missing and below level of quantification (BLQ) values.

For PD data analysis, there will be no imputation for missing values.

If medication dates are incomplete and it is not clear whether the medication was concomitant, it will be assumed to be concomitant.

AEs with unknown start date/time will be assumed to be treatment-emergent unless the end date/time is known to be before the first administration of study drug. Otherwise missing or partial dates will be listed as such.

There will be no further imputation of missing data (i.e., subjects who prematurely discontinue from the study will not be included in summary statistics or analyses beyond the time of discontinuation).

Depending on the extent of missing values, the appropriateness of the methods described for handling missing data may be reassessed prior to database lock (to examine the sensitivity of results to handling of missing data).

Certificate Of Completion

Envelope Id: PPD

Subject: Please DocuSign: C18054 ALXN1840-HV-104 SAP Final 1.0 11Nov2019 signed.pdf

Source Envelope:

Signatures: 2 Document Pages: 20 Certificate Pages: 2 Initials: 0

AutoNav: Enabled

Envelopeld Stamping: Disabled

Time Zone: (UTC-05:00) Eastern Time (US & Canada)

Status: Completed

Envelope Originator:

PPD

[name]

Sent: 19-Nov-2019 | 13:00 Viewed: 19-Nov-2019 | 13:20 Signed: 19-Nov-2019 | 13:21

Sent: 19-Nov-2019 | 13:00

PPD

IP Address: PPD

Record Tracking

Holder: PPD Status: Original Location: DocuSign

19-Nov-2019 | 12:54

Signature Signer Events **Timestamp**

Security Level: Email, Account Authentication

(Required), Digital Certificate

Alexion Pharmaceuticals Inc.

Signature Provider Details: Signature Type: Alexion Pharmaceuticals, Inc.

(Regulated) (Client ID: PPD

PPD

PPD

Signature Issuer: Alexion Pharmaceuticals Issue https://dswebapp.alexion.com/takepen/signenvelope 2 CA

Signature Adoption: Pre-selected Style

Signature ID:

PPD

Using IP Address: PPD

Signature Provider Location:

With Signing Authentication via DocuSign password

With Signing Reasons (on each tab):

